### Data analysis

We will first present the distribution of the SWD for all patients and estimate the mean and standard deviation (SD) of the SWD, or the median SWD with its interquartile range (IQR) depending on distribution skewness. The 95% CI will also be presented. Then we will present the distribution of SWD in subgroups for the various patient, treatment, and condition characteristics (predictors). These characteristics will be included in a regression model to evaluate whether they are associated with variability in the SWD. As the SWD is estimated as a continuous variable we will examine whether the distribution is compatible with the normal distribution. If not, transformation using a link function  $f$  will be considered. Then a standard linear regression model, using the predictors will be estimated. Model selection will be performed using the least absolute shrinkage and selection operator (LASSO) method (Tibshirani, 1996). When important subgroup differences are found, we will present the SWD for such subgroups. To determine if the two survey methods equally estimate the SWD, we will compare the total average SWDs of the *high-to-low* and *back-and-forth* BHTM methods with a  $t$  test. All statistical analyses will be performed using R software (Statistical Computing, Vienna, Austria) or SAS (Cary, NC, SAS Institute Inc).

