**Supplement 2. Changes from the Protocol**

Due to our stringent quality screening process, we were unable to recruit enough responses from Mechanical Turk (MTurk) alone. This was first approved by the IRB August 9th, 2022 (R3574). We added two other research participant crowdsourcing services (Prolific, MQ) and included UK residents, which was approved September 9th, 2022 (R3574-1). Second, at the time of protocol writing, we had not anticipated that there would be people who would never consider antidepressants worthwhile, even if they brought about 100% response. We therefore made a post hoc decision to prioritize practical interpretation and exclude such people from our primary analysis but run sensitivity analyses including them. Finally, because the two types of the BHTM scripts originally included in the questionnaire produced similar estimates, we considered all responses to equally represent the SWD in the analyses.

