**Supplement 5. Benefit-Harm Tradeoff Method Algorithm Testing and Sample Size Calculation**

We used two separate methods within the BHTM for determining the participants' SWD: the *high-to-low* method and the *back-and-forth* method (see Supplements 3 and 4). Both methods have been employed in the SWD literature (See Ferreira et al., 2012 and McNamara et al., 2015), and the most accurate SWD estimation had not been determined. Therefore, we opted to randomly allocated participants 1:1 to each method to see if they differed in their estimation. Our original sample size estimate for the SWD and its 95% CI for 4 clinical subgroups, required 780 participants based on population estimates. However, testing the difference between two separate methods required double the estimate. Based on subgroup populations, approximately N=1,600 participants were thought to be necessary to reach a minimum of n=80 in all 8 subgroups.

After we reached a minimum number of participants per group, we compared the SWD between methods. We found the difference between methods was 3.6 percentage points and we used 5 percentage point increments for the SWD. Thus, we determined both methods to be equally appropriate and all participants were analyzed together. Recruitment was stopped after all subgroups included n=80.

**Supplement 6.** Associations between demographic and clinical variables and SWD

	Univariable regression		Multivariable regression	
	Coefficient	95%CI	Coefficient	95% CI
Demographic Variables				
Age	0.050	-0.021 to 0.12	0.069	-0.03 to 0.16
Sex				
Male	ref		ref	
Female	-0.61	-2.75 to 1.53	-1.66	-4.01 to 0.67
Non-binary	1.66	-7.23 to 10.56	1.43	-7.75 to 10.61
Race				
White/Caucasian	ref		ref	
Black/African American	2.22	-2.53 to 6.97	3.57	-1.29 to 8.43
Asian	2.74	-2.40 to 7.89	3.33	-2.06 to 8.71
Latino/Hispanic	3.69	-1.98 to 9.35	6.55	0.62 to 12.47
Multiracial	2.27	-4.45 to 8.90	3.71	-3.00 to 10.42
Other	1.42	-8.86 to 11.70	0.90	-9.40 to 11.19
Education				
Less than high school	3.78	-2.36 to 9.92	2.61	-3.74 to 8.94
High school graduate/Equivalent	0.36	-2.96 to 3.69	0.04	-3.35 to 3.44
Some college	-0.61	-3.18 to 1.96	-1.16	-3.87 to 1.54
2-year degree	-3.23	-6.56 to 0.10	-2.76	-6.15 to 0.63
4-year degree	ref		ref	
Master's degree	-0.86	-4.45 to 2.73	-1.74	-5.34 to 1.86
Doctorate	-4.04	-11.25 to 3.17	-4.09	-11.26 to 3.08
Employment				
Disabled	3.62	-0.36 to 7.60	4.08	-0.23 to 8.40

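### Supplement 6 reports a full 31-coefficient model where LASSO selection was planned, the change list does not say so, and no joint factor tests support its isolated race and employment categories

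*Combined protocol and SAP*

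**What the plan says.** The Data analysis section of the protocol gives the regression this purpose: "These characteristics will be included in a regression model to evaluate whether they are associated with variability in the SWD". The steps follow in order. First comes a full fit: "Then a standard linear regression model, using the predictors will be estimated". Then comes selection: "Model selection will be performed using the least absolute shrinkage and selection operator (LASSO) method". A reporting rule follows: "When important subgroup differences are found, we will present the SWD for such subgroups". The section does not state how the LASSO penalty is chosen, whether the model is refitted after selection, how the dummies of a multi-category factor are handled, or what makes a difference important. The only interval it names belongs to the overall SWD summary: "The 95% CI will also be presented".

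Supplement 6, titled "Associations between demographic and clinical variables and SWD", has a univariable and a multivariable column with a coefficient and 95% CI for every listed term. It has no joint test per factor, no p values and no significance marks.

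Supplement 2 lists the changes from the protocol. It covers recruitment ("Due to our stringent quality screening process, we were unable to recruit enough responses from Mechanical Turk (MTurk) alone"), the post hoc exclusion of respondents who would never find antidepressants worthwhile, and the pooling of the two question methods ("Finally, because the two types of the BHTM scripts originally included in the questionnaire produced similar estimates"). It does not mention the regression or LASSO.

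**The concern.** Two things do not fit together. The plan commits to a selection step, but the reported table keeps every term, even one as close to null as High school graduate (0.04, -3.35 to 3.44). A document written to list departures is silent on it. A reader cannot tell whether the selection was dropped, was run and reported elsewhere, or was run and not reported.

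The second matter is how the table will be read. The protocol's Expected Results section anticipates variation in the SWD between clinical and demographic subgroups, so readers will look for it here. Race, education, employment, insurance, sex and clinical group each enter as several dummies against a chosen reference. Without a factor-level test, one category whose interval excludes 0 can be taken as an ethnicity or employment effect of about 6 percentage points. That is larger than the 5-point increment used in the survey (Supplement 5). The overall SWD estimate is not affected.

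**Working it through.** **1. Count of terms in Supplement 6.** Age 1, sex 2, race 5, education 6, employment 6, country 1, insurance 4, clinical group 3, lifetime depression 1, family history 1, treatment preference 1. The sum is 31 terms from 11 factors, 6 of them multi-category. All 31 have a multivariable coefficient and CI, so no term was dropped.

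**2. Type of interval.** Each coefficient lies at the midpoint of its CI to within rounding (largest gap 0.045). The intervals therefore look like ordinary symmetric ones from an unselected fit.

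**3. Single-term results.** SE = CI width / 3.92, z = coefficient / SE.

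| Term (multivariable) | SE | z | p |
|---|---|---|---|
| Latino/Hispanic | (12.47 - 0.62)/3.92 = 3.02 | 6.55/3.02 = 2.17 | 0.030 |
| Unemployed and looking | (10.38 - 0.84)/3.92 = 2.43 | 5.61/2.43 = 2.31 | 0.021 |
| Prefers antidepressants | (7.19 - 2.73)/3.92 = 1.14 | 4.95/1.14 = 4.35 | 0.00001 |

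These are the only 3 of 31 intervals that exclude 0. If all terms were null, 31 x 0.05 = 1.55 would be expected. Bonferroni within factor gives 5 x 0.030 = 0.15 for race and 6 x 0.021 = 0.13 for employment.

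**4. Approximate joint tests.** Let b be the coefficients of one factor and W = b'V⁻¹b, referred to chi-square with as many df as categories less one. The covariances are not printed, so I take V = diag(SE² - c) + c·11', where c is the variance of the reference-category mean that all contrasts share. This form is exact for a one-factor model and approximate here. c must lie between 0 and the smallest SE² in the factor: 6.15 for race, 2.11 for employment.

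| c | Race W (5 df) | p | Employment W (6 df) | p |
|---|---|---|---|---|
| 0 | 9.44 | 0.093 | 12.89 | 0.045 |
| 0.3 | 8.59 | 0.127 | 10.37 | 0.110 |
| 0.5 | 8.12 | 0.150 | 9.31 | 0.157 |
| 1.0 | 7.20 | 0.206 | 7.71 | 0.260 |
| 2.0 | 6.04 | 0.303 | 6.67 | 0.353 |

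Over its whole feasible range, race p runs from 0.09 to 0.42 and employment p from 0.045 to 0.35.

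**5. Can c be close to 0?** Employment p is below 0.05 only if c is below about 0.03. Since c = σ²/n_ref is at least σ²/N, that would need σ²/N below 0.03. For a binary predictor, SE² = σ²/[N·p(1-p)]. Lifetime depression has univariable SE (1.17 + 2.85)/3.92 = 1.026, so SE² = 1.05. Then p(1-p) would be below 0.03/1.05 = 0.029, a split more extreme than about 3:97. That is hard to credit in this sample.

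**6. If LASSO is kept.** Ordinary intervals on selected terms would under-cover. For a null term in an orthogonal design that is kept when |z| exceeds t, coverage is 1 - 0.05/P(|Z|>t). This gives 1 - 0.05/0.317 = 84% at t = 1 and 1 - 0.05/0.134 = 63% at t = 1.5. Both thresholds are assumptions, because the plan gives no penalty rule.

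**The case against.** Several points on the other side stand.

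- A reader might infer that the plan produces invalid intervals. It does not plan intervals for LASSO-selected coefficients at all. The fair statement is that tuning, refit and inference are unspecified, and that ordinary intervals would under-cover if they were used. The Supplement 6 intervals appear to be unselected, so this does not touch the printed results.
- The under-coverage is conditional on selection and does not imply more false exclusions in total. At t = 1, 31 x 0.317 x (0.05/0.317) = 1.55, the same count that the full model gives.
- The protocol itself plans a full linear model before selection, so a full table is a planned output. What is missing is any sign of the selection. The main report is not among these documents and may contain it, so a reader who concludes that LASSO was replaced is inferring.
- Supplement 6 marks nothing as significant and highlights no category. The risk lies in how it is read.
- A reader might also infer that race and employment are unrelated to the SWD. A non-significant joint test does not show that, and these tests are approximations.
- The clinical subgroups are prespecified and sized, and subgroup distributions are to be presented before any regression. The regression is therefore not the only route to a subgroup SWD.

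Defining importance by unadjusted F tests on all 11 factors would be a matter of preference. It carries a chance of 1 - 0.95^11 = 43% of at least one false positive if the factors were independent and null, so it is not proposed here. None of these points explains the silence in Supplement 2 or supplies a factor-level test.

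**Conclusion.** The point holds in a limited form. LASSO selection was planned, the supplements show a full 31-term model, and the change list does not account for the difference. Two of the three multivariable intervals that exclude 0 are isolated categories, and the printed values give no clear evidence for their factors: race p about 0.09 to 0.42, and employment p about 0.045 to 0.35, below 0.05 only if the shared reference variance is almost nil. Treatment preference is a one-df factor with strong evidence and is unaffected.

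The joint p values rest on normal-theory SEs taken from the CIs and on a covariance form that is only approximate for the multivariable model. The exact tests need the fitted covariance matrix. The matter concerns a secondary association analysis and does not alter the main SWD estimate.

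**What to change.** 1. In Supplement 2, state that the full model was reported in place of LASSO selection, and why. If LASSO was run, report its result instead.
2. In Supplement 6, add a joint F test p value for each of the six multi-category factors (sex, race, education, employment, insurance, clinical group), and say that single-category contrasts are descriptive.
3. If LASSO is kept, state how the penalty is chosen, use the grouped version so that selection does not depend on the reference category, and do not attach ordinary CIs to selected terms.

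The first two items cost one line in the change list, one table note and six tests on a model already fitted; no new data are needed. The drawback is that fewer category-level differences can be presented as findings.

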### Expected Results

We expect to find an estimate of the SWD for antidepressants in the treatment of depression for the first time in the long history of human psychopharmacology. Further, we expect that the SWD will vary between clinical and demographic subgroups. In particular, we expect there to be variation between those who demonstrate depression symptoms consistent with a depressive disorder, based on PHQ-9 scores or self-reported diagnosis history. We hope that the findings from this project will inform the controversies about the worthiness of antidepressants for depression.

**Supplement 2. Changes from the Protocol**

Due to our stringent quality screening process, we were unable to recruit enough responses from Mechanical Turk (MTurk) alone. This was first approved by the IRB August 9th, 2022 (R3574). We added two other research participant crowdsourcing services (Prolific, MQ) and included UK residents, which was approved September 9th, 2022 (R3574-1). Second, at the time of protocol writing, we had not anticipated that there would be people who would never consider antidepressants worthwhile, even if they brought about 100% response. We therefore made a post hoc decision to prioritize practical interpretation and exclude such people from our primary analysis but run sensitivity analyses including them. Finally, because the two types of the BHTM scripts originally included in the questionnaire produced similar estimates, we considered all responses to equally represent the SWD in the analyses.

**Supplement 3. Smallest Worthwhile Difference Survey Script****PART 1**

**The next five slides include information on depression and its treatment. Please carefully read them and keep this in mind when answering the questions after the Information.**

**1. CLINICAL DEPRESSION**

Everyone feels “depressed” from time to time. However, clinical depression is a more serious condition lasting much longer. When clinical depression is moderate to severe, symptoms such as the following are present nearly every day for a minimum of two weeks, and often for several months:

- Feelings of sadness, tearfulness, emptiness, or hopelessness
- Loss of interest or pleasure in most or all normal activities, such as hobbies, sports or sex
- Reduced appetite and weight loss or conversely, increased cravings for food and weight gain
- Anxiety, agitation, or restlessness
- Sleep disturbances, including insomnia or sleeping too much
- Slowed thinking, speaking, or body movements
- Tiredness and lack of energy, so even small tasks may require extra effort
- Feelings of worthlessness or guilt, fixating on past failures or self-blame
- Trouble thinking, concentrating, making decisions, and remembering things
- Frequent or recurring thoughts of death, suicidal thoughts, or suicide attempts
- Unexplained physical problems, such as back pain or headaches

Not everyone who is depressed experiences every symptom. Some people experience only a few symptoms while others may experience many. Symptoms are usually severe enough to cause noticeable problems with relationships, work, school, at social activities.

**2. TREATMENT OF CLINICAL DEPRESSION**

[figure not shown]
There are many different approaches to treating depression, but in this study, we will only focus on (1) no treatment (i.e., natural recovery) and (2) antidepressant drugs. First, I will describe each treatment option's expected benefits and drawbacks. Then I will ask if you think antidepressant treatment is worthwhile at different levels of patient benefit.

**3. No Treatment (Natural Recovery)**

By declining all treatment, about 30/100 people can expect to feel much better after 8 weeks, on average.

### No Treatment

30/100 People Feel Much Better

#### **4. Antidepressant Drugs**

Antidepressants are medicines that treat clinical depression. They help regulate the way our brain manages mood and stress. Antidepressants usually take 2 to 4 weeks to work. Depending on insurance plans, monthly expenses can range from \$0-\$350 USD equivalent (100 USD  $\approx$  84 GBP/96 EUR/149 AUD), covering office/clinic visits, prescription expenses, and transportation. As with all prescriptions, antidepressants may cause side effects. If side effects occur, they are mostly temporary and mild. The most common side effects listed by the US government (FDA) include:

- nausea
- nervousness
- insomnia
- sexual problems
- tremor (shaking)
- sweating
- agitation
- feeling tired
- dry mouth
- constipation

Serious side effects are very rare, happening in less than 1% of patients. Patients are directed to call their doctor if they experience any of the following rare symptoms:

- seizures
- abnormal bleeding or bruising
- increase in blood pressure

Antidepressants may cause other side effects that were not included in this list. Ending antidepressant prescriptions should be done slowly and under doctor supervision because abruptly stopping can cause withdrawal symptoms like anxiety, insomnia, headaches, tiredness, irritability, or flu-like symptoms.

#### **5. Reminder**

There are many different approaches to treating depression, but please assume you only have two choices when deciding to relieve depressive symptoms: antidepressant medications versus no treatment. Do not consider any other alternatives in your decision.

First, consider the possible drawbacks that have been mentioned (side effects, medical and prescription expenses, and other inconveniences). Then, weigh the drawbacks relevant to you with the presented hypothetical benefits when answering the following questions.

## PART 2

---

Given the potential drawbacks after 8 weeks, if **100/100** people taking antidepressant medications felt much better (instead of 30/100 from no treatment), would you think the treatment is worthwhile?

[figure not shown]

**IF NO = Survey complete, respondent does not believe antidepressants are worthwhile at any effect**

**IF YES = Follow algorithm to next hypothetical effect**

[figure not shown]
**Responses follow one of two different randomly assigned algorithms presented in Supplement 4.**

**Supplement 4. Question Sequence Algorithms**  
**4a. Back-and-Forth Benefit Harm Tradeoff Method**

[figure not shown]
4b. High-to-Low Benefit Harm Tradeoff Method

- Yes, it is worthwhile
- No, it is not worthwhile

**Supplement 5. Benefit-Harm Tradeoff Method Algorithm Testing and Sample Size Calculation**

We used two separate methods within the BHTM for determining the participants' SWD: the *high-to-low* method and the *back-and-forth* method (see Supplements 3 and 4). Both methods have been employed in the SWD literature (See Ferreira et al., 2012 and McNamara et al., 2015), and the most accurate SWD estimation had not been determined. Therefore, we opted to randomly allocated participants 1:1 to each method to see if they differed in their estimation. Our original sample size estimate for the SWD and its 95% CI for 4 clinical subgroups, required 780 participants based on population estimates. However, testing the difference between two separate methods required double the estimate. Based on subgroup populations, approximately N=1,600 participants were thought to be necessary to reach a minimum of n=80 in all 8 subgroups.

After we reached a minimum number of participants per group, we compared the SWD between methods. We found the difference between methods was 3.6 percentage points and we used 5 percentage point increments for the SWD. Thus, we determined both methods to be equally appropriate and all participants were analyzed together. Recruitment was stopped after all subgroups included n=80.

**Supplement 6.** Associations between demographic and clinical variables and SWD

	Univariable regression		Multivariable regression	
	Coefficient	95%CI	Coefficient	95% CI
Demographic Variables				
Age	0.050	-0.021 to 0.12	0.069	-0.03 to 0.16
Sex				
Male	ref		ref	
Female	-0.61	-2.75 to 1.53	-1.66	-4.01 to 0.67
Non-binary	1.66	-7.23 to 10.56	1.43	-7.75 to 10.61
Race				
White/Caucasian	ref		ref	
Black/African American	2.22	-2.53 to 6.97	3.57	-1.29 to 8.43
Asian	2.74	-2.40 to 7.89	3.33	-2.06 to 8.71
Latino/Hispanic	3.69	-1.98 to 9.35	6.55	0.62 to 12.47
Multiracial	2.27	-4.45 to 8.90	3.71	-3.00 to 10.42
Other	1.42	-8.86 to 11.70	0.90	-9.40 to 11.19
Education				
Less than high school	3.78	-2.36 to 9.92	2.61	-3.74 to 8.94
High school graduate/Equivalent	0.36	-2.96 to 3.69	0.04	-3.35 to 3.44
Some college	-0.61	-3.18 to 1.96	-1.16	-3.87 to 1.54
2-year degree	-3.23	-6.56 to 0.10	-2.76	-6.15 to 0.63
4-year degree	ref		ref	
Master's degree	-0.86	-4.45 to 2.73	-1.74	-5.34 to 1.86
Doctorate	-4.04	-11.25 to 3.17	-4.09	-11.26 to 3.08
Employment				
Disabled	3.62	-0.36 to 7.60	4.08	-0.23 to 8.40
Homemaker	1.51	-3.50 to 6.51	1.89	-3.21 to 6.98
Retired	2.93	-0.57 to 6.42	2.10	-2.26 to 6.46
Student	1.52	-3.55 to 6.59	1.83	-3.65 to 7.32
Unemployed and looking	4.88	0.21 to 9.54	5.61	0.84 to 10.38
Working full-time	ref		ref	
Working part-time	1.39	-1.29 to 4.06	2.20	-0.65 to 5.04
Country				
UK	ref		ref	
US	-2.39	-4.43 to -0.34	-0.46	-4.32 to 3.41
Insurance				
Affordable Care Act/Obamacare	-3.55	-10.33 to 3.23	-3.92	-11.65 to 3.82
Medicare/Medicaid	-4.21	-7.99 to -0.43	-5.19	-10.52 to 0.14
National Healthcare Insurance	ref		ref	
Private Health Insurance	-2.42	-4.95 to 0.11	-3.03	-7.08 to 1.01
Uninsured	-1.07	-3.66 to 1.53	-1.56	-4.25 to 1.13
Clinical Variables				

Group				
Currently Depressed but Not Treated	ref		ref	
Currently in Treatment	1·96	-1·25 to 5·17	2·70	-0·83 to 6·22
Euthymic with Treatment Experiences	1·62	-2·53 to 5·77	2·30	-2·00 to 6·61
Euthymic without Treatment Experiences	2·80	-0·52 to 6·13	2·23	-1·56 to 6·02
Lifetime Depression	-0·84	-2·85 to 1·17	-0·91	-4·47 to 2·66
Family History of Depression	-0·01	-2·03 to 2·02	1·14	-1·02 to 3·30
Treatment Preference				
Antidepressants	-4·32	-6·35 to -2·30	-4·95	-7·19 to -2·73
Psychotherapy	ref		ref	

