### Sample Size

Sample size was calculated to achieve expected precision in the estimates of the SWD. Because there has been no study to estimate SWD for depression and its SD is unknown, we substituted it with the SD of SWD for pain also measured on a scale of 0-100: this study suggested an SD of 22 for SWDs of 20% (Ferreira et al., 2013). Assuming a similar SD, and to obtain a 95% confidence interval within 10 points, approximately 80 respondents per group are needed. We will also randomly assign participants to either the *high-to-low* or *back-and-forth* BHTM methods, which will require twice the respondents per method to determine differences between the methods with 160 respondents per group (80 respondents x 2 methods). Since we are estimating SWD and its 95% CI for 4 subgroups (see respondent recruitment above), 640 respondents are needed (160 respondents x 4 groups). This should be enough to examine all the pre-specified potential predictors (see Data analysis below) (Austin & Steyerberg, 2015).

The survey will be piloted with 300 respondents to determine if the population distribution estimate is appropriate to reach  $n = 160$  in all four subgroups. We have estimated that approximately 20% of the respondents will screen positive for moderate to severe depressive symptoms with the PHQ-9. This is greater than the general population, but still a conservative estimate for MTurk subgroups, which have been shown to demonstrate up to 3.6 times greater depression point prevalence than the general population (Ophir et al., 2020). Based on this estimated MTurk-specific subgroup populations, approximately 1,600 respondents may be necessary to reach 80 in the subgroups with the smallest populations (see Figure 1). If more respondents are needed, recruitment will continue until 80 people per subgroup are reached.

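### The two elicitation methods are called equally appropriate because their 3.6-point difference is below the 5-point answer step, a rule that ignores sampling error and does not show agreement

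*Combined protocol and SAP*

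**What the plan says.** The protocol's Data analysis section states: "To determine if the two survey methods equally estimate the SWD, we will compare the total average SWDs", and names a t test for the purpose. It gives no margin, significance level or sidedness.

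Supplement 5 describes the allocation: "we opted to randomly allocated participants 1:1 to each method to see if they differed in their estimation". For the result it gives one sentence: "We found the difference between methods was 3.6 percentage points and we used 5 percentage point increments for the SWD". The conclusion follows directly: "Thus, we determined both methods to be equally appropriate and all participants were analyzed together".

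Supplement 2 repeats the conclusion as the reason for a change from the protocol: "because the two types of the BHTM scripts originally included in the questionnaire produced similar estimates". All responses were then taken to represent the SWD equally.

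For this comparison the documents give no mean, SD, n, SE, confidence interval or p-value by method. The Supplement 6 regressions have no term for method.

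**The concern.** Two things are wrong with the stated rule. First, the 5-point increment limits how finely one respondent can answer. The mean of several hundred such answers is known far more precisely than that, so the increment says nothing about how large a difference between two means can be ignored. Second, the rule looks only at the point estimate. The same 3.6 points could be noise in a small sample or a clear method effect in a large one, and the rule would pass both.

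The planned t test would not have settled the matter either. A non-significant result does not show equality, and a significant one shows a difference. A claim that two methods agree needs a confidence interval set against a margin chosen on its merits.

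At stake is how the headline value is read. If the methods differ, the SWD depends on how the question is asked, and the reader should see by how much. A difference of 3.6 points is 18% of an SWD of 20 (3.6/20) and 14% of 25 (3.6/25), the two values used in Supplement 7. The protocol's introduction intends the SWD as a benchmark for new therapies.

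**Working it through.** **Inputs.** Difference 3.6 points, increment 5 points, 1:1 allocation, minimum of 80 in each of 8 subgroups and expected N of about 1,600 (Supplement 5). From Sample Size in the protocol: "this study suggested an SD of 22 for SWDs of 20" (percent), and "to obtain a 95% confidence interval within 10 points, approximately 80 respondents per group are needed". A two-sided 5% level is assumed, since none is stated.

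**The plan's own figure.** Reading the precision target as a half-width of 5, n = (1.96 × 22 / 5)² = 74.4, so 75. The plan rounds this up to about 80, which gives a half-width of 1.96 × 22 / √80 = 4.8. Then 80 × 2 methods × 4 groups = 640, as stated. The 3.6 itself cannot be re-derived, because no method-specific figures are given.

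**SE from the planning SD.** SE = SD × √(2 / n per method).
- N = 640: 22 × √(2/320) = 1.74
- N = 1,600: 22 × √(2/800) = 1.10

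**SE from Supplement 6.** Univariable 95% CI width divided by 3.92:
- lifetime depression: (1.17 + 2.85)/3.92 = 1.026
- family history: (2.02 + 2.03)/3.92 = 1.033
- treatment preference: (6.35 − 2.30)/3.92 = 1.033
- country: (4.43 − 0.34)/3.92 = 1.043

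For a given sample and SD, a 1:1 split has the smallest SE of any two-group split. In the Supplement 6 sample, the SE of the method difference would therefore be about 1.03 or less.

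**Results for a difference of 3.6.** TOST is two one-sided tests against ±5. That margin is used only because it is the figure Supplement 5 relies on.

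| Basis | SE | 3.6/SE | p | 95% CI | 90% CI | TOST p |
|---|---|---|---|---|---|---|
| SD 22, N = 640 | 1.74 | 2.07 | 0.039 | 0.2 to 7.0 | 0.7 to 6.5 | 0.21 |
| SD 22, N = 1,600 | 1.10 | 3.27 | 0.001 | 1.4 to 5.8 | 1.8 to 5.4 | 0.10 |
| Supplement 6 | 1.03 | 3.5 | 0.0005 | 1.6 to 5.6 | 1.9 to 5.3 | 0.09 |

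In the last row the SE is an upper bound, so both p-values are upper bounds too.

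**Where the conclusions would change.**
- Significance is lost if the SE exceeds 3.6/1.96 = 1.84. At SD 22 that means fewer than 2 × (22 × 1.96/3.6)² = 287 per method. With 160 per method, SE = 2.46 and p = 0.14.
- Equivalence within 5 points needs an SE below (5 − 3.6)/1.645 = 0.85. At SD 22 that is 2 × (22/0.851)² ≈ 1,337 per method, or a total N of about 2,670.
- An SE of 0.85 in the Supplement 6 sample would require all four binary predictors above to be split about 22:78 or more unevenly. Supplement 6 gives no category counts, so this cannot be ruled out, but it is unlikely.

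**Scale.** Around an SWD of 20, values of 18.2 and 21.8 give response rates of 48.2% and 51.8% against 30%, so ORs of 2.17 and 2.51. With SMD = (√3/π) × ln(OR) = 0.551 × ln(OR), these become 0.43 and 0.51.

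**The case against.** The strongest reply is that significance is inferred, not reported. The SD of 22 comes from a pain study, and the N at the time of the comparison is not stated beyond a minimum per group having been reached. The Supplement 6 sample may also differ, for example by leaving out respondents who would never find treatment worthwhile. This stands, and the result is conditional for that reason. It does not rescue the rule: a smaller sample weakens significance but moves equivalence further away.

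A reader might infer more than the documents support:
- **That the t test was dropped.** Supplement 5 says the methods were compared, not how, and these documents are the supplement to a report. Only the absence of a result here can be stated.
- **That equivalence within 5 points has failed.** The Supplement 6 route bounds the SE from above, so it bounds the TOST p from above. Failure would need a lower bound.
- **That the pooled mean is wrong.** With 1:1 allocation it is already close to the equal-weight average of the two methods.
- **That the Supplement 6 coefficients are biased.** Leaving out a randomised method term does not bias them in expectation.
- **That method outweighs the other predictors.** It exceeds the univariable group contrasts (1.62 to 2.80) and country (−2.39), but treatment preference (−4.32), Medicare/Medicaid (−4.21) and unemployed (4.88) are larger. The group intervals also reach 5.17 to 6.13.
- **That 3.6 is certainly free of confounding.** Supplement 3 places the exit question before the two sequences. However, the algorithm figures are not shown, and the timing of quality screening relative to assignment is not given.

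It can also be said that ±5 echoes the planned precision, and that Supplement 7 already shows a wider range (SWD 20 and 25, SMD 0.47 and 0.58). Neither point makes the answer increment a justified margin. The documents do openly state the randomisation, the 3.6 and the reason for pooling.

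**Conclusion.** The stated basis for treating the methods as interchangeable does not hold. This conclusion needs no assumption about the sample: the increment is not a margin, and no measure of uncertainty is given.

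The size is conditional. If the comparison used the planned sample or roughly the Supplement 6 sample, the 3.6-point difference is statistically significant, with p from about 0.04 to 0.0005 and lower 95% limits of 0.2 to 1.6 points. Equivalence within 5 points is not shown and probably not met, since it would need an SE below about 0.85 where the available figures point to 1.03 to 1.74.

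Pooling itself can be defended as a deliberate average over two ways of asking. What cannot be defended on these figures is the claim that the two ways give the same answer. These figures concern a difference in means. The Data analysis section also allows a median as the headline, and the effect of method on the median is unknown.

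**What to change.** 1. Report the planned t test with its 95% confidence interval and the n per method, and state which sample was used.
2. Report the SWD for each method, as mean and median, beside the pooled value.
3. Remove the claims of equal appropriateness (Supplement 5) and similar estimates (Supplement 2), unless an equivalence test supports them, with the 90% confidence interval inside a margin justified on grounds other than the answer increment.
4. If pooling is kept, describe it as an explicit average over the two methods and give the method-specific values as its range.
5. Optionally, add the randomised method as a term in the Supplement 6 models.

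The cost is a short re-run on data already held and some rewording. The downside is that the headline SWD will visibly depend on method by about 3.6 points.
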